7.3 Lost to Follow-Up

This is an orthopedic trial. The surgery is the start point and after the surgery there are no treatments. There are only follow-up visits, which include an MRI and 3 questionnaires (IKDC, KOOS, CRF). Follow-up-visits are at the end of the hospital stay, 6 weeks after surgery (both for operated patients only), and then for all patients: after 6, 12 and 24 months and after 5 years.

Lost to follow-up will occur because the trial population are mainly young active people. They will move for work or private reasons and may not finish the visits. In the number of patients for the trial lost to follow-up is included in the statistical calculations. The investigator will explain, when the informed consent is discussed with the patient, the importance of attending the follow-up-visits. If the investigator has the impression that the patient will not be compliant regarding the follow-up-visits, he will not include the patient in the trial.

When a patient is lost to follow up, the data up to the last visit attended will be used.

7.4 Trial Stopping Rules

If AE, SAE and SUSARs change the benefit-risk balance, there will be a new benefit-risk balance evaluation and after this evaluation it will be decided if the trial will be stopped.

If the safety of the patients is not any more given, the trial should be stopped.

The investigator expects a maximal 20% failure rate of the procedure. If the failure rate is higher a new benefit-risk balance evaluation must be performed and after the evaluation it must be decided if the trial continues.

The investigator also has the right to stop the trial. This could be because of the closure of the site. See 10.5 for details.

8 TRIAL ASSESSMENTS AND PROCEDURES

Assessment procedure is described in detail under 1.2 trial scheme and under 1.3 schedule of activities.

8.1 Screening/Baseline Assessments and Procedures

The recruitment of patients for the investigator-initiated trial takes place during the consultation hours of the study centre. Since patients are specifically assigned for partial meniscus implantation, patients are already informed about the investigator-initiated trial at the time of appointment.

During the first visit (Screening) an MRI is done and evaluated, the inclusion and exclusion criteria are verified. If the patient qualifies for participation in the study based on the inclusion and exclusion criteria, he/she will be informed about the therapeutic procedure of partial meniscus implantation with Spongioflex® and the planned investigator-initiated trial (planned visits, data protection, etc.) will be explained. Patients also receive an information sheet explaining the surgical procedure, the advantages and disadvantages, the risks, and the follow-up treatment. After a sufficient reflection period, the patient must sign the informed consent form for participation in the investigator-initiated trial and the data protection declaration. Without these written consents, inclusion in the investigator-initiated trial cannot take place. After the signatures, the patient is included in the investigator-initiated trial. At this time point the patient must decide if he wants to be operated or not. In accordance with standard clinical practice, the usual risk information for the surgical procedure is provided for patients who decided to be operated. This is conducted based on the information sheet customary in the respective hospital. In this form, patients are usually informed about the procedure, the treatment alternatives, the risks, and the aftercare. Women are treated in the same way. Spongioflex® does not affect the body's metabolism and does not influence the effect of medications the patient is taking, thus there is no need for special female treatment options. There is no restriction for medication taken by the patient. For the control group (not operated patients) the follow-up visits are explained.

- Pregnant women are excluded from surgery
- Minor patients are not included

8.2 Efficacy Assessments and Procedures

The surgical procedure will be assessed at any time. The procedure should be successful in at least 80% of the patients. If there is a failure rate of more than 20 % the benefit-risk balance evaluation will be renewed. If the risk overweight's the benefit of the surgical procedure, the trial will be prematurely terminated. For this reason, close meshed follow-up is scheduled to obtain sufficient information regarding the efficacy of the surgical procedure.

8.3. Safety Assessments and Procedures

This is a low intervention trial. This trial poses a minimal additional risk to subject safety compared to normal clinical practice (CTR, page 2 (11)).

As described under 8.2 there is a close-meshed follow-up schedule, for operated patients, which will also evaluate the patient's safety. The highest risk that safety issues occur is during surgery. But the surgery is an established method. All safety measures will be taken during surgery as for every surgery, not being a clinical trial. The first visit at the end of the hospital stay is one of the safety measures for the patient. Before the patient leaves the hospital, the patient will be checked, if there are no issues which may affect his/her safety. AE, SAE and SUSARs are recorded in the electronic patient chart and will be recorded in the CRF.

AE will only be recorded in the electronic patient chart and in the CRF. When AEs affecting the conduct of the trial and/or increasing the risk to the subject, the IRB/IEC should be promptly informed by a written

report.

SAE: because the investigator and sponsor is the same person in this trial, information to the sponsor is immediately. The SAE will be recorded in the electronic patient chart and in the CRF. Unless the protocol waives the notification, the investigator reports the SAE to the ethic committee and to the local authorities (Bundesoberbehörde) immediately but at least within 15 days, after becoming aware of it. If the investigator does not have all the information by then, the missing information must be submitted as soon as possible.

SUSARs: The investigator/sponsor shall inform the competent higher federal authority, the lead ethics committee, and the competent authorities of other Member States immediately, but at the latest within 15 days of becoming aware of a SUSAR. The deadline is reduced to 7 days if an unexpected serious adverse reaction is life-threatening or has led to death.

There are no laboratory investigations part of the trial.

There is no independent Data Monitoring Committee. Clinical monitoring will be performed from an independent clinical monitor for the safety of the patients. The extend and nature of the monitoring will be adapted due to Article 48 CTR.

8.3.1 Physical Examination

Physical examinations will be performed at each visit. Normal evaluations will not be recorded, only adverse events and complications.

8.3.2 Vital Signs

Vital signs are only recorded before and during surgery. The IMP has no systemic effect. For this reason, vital signs are recorded and not evaluated in the follow-up visits.

8.3.3 Electrocardiograms

Electrocardiograms are only recorded before and during surgery. The IMP has no systemic effect. For this reason, vital signs are not recorded and evaluated in the follow-up visits.

8.3.4 Clinical Laboratory Assessments

Clinical laboratory assessment will only be performed before surgery, due to normal medical praxis to prepare surgery. After the surgery, a laboratory assessment will only be performed, when AE (e.g. infections) are recorded or other events which need laboratory assessment. This will be due to routine practice of the hospital, where the patient is located or due to the practice of the investigator for such events and is not related to a special laboratory assessment due to the clinical trial

8.3.5 Suicidal Ideation and Behaviour Risk Monitoring

The diagnosis of partial meniscal defect is not life-threatening, thus suicidal ideation is not common for this kind of diagnosis. As described in 8.2, a close meshed follow-up is scheduled after surgery. The KOOS questionnaire includes questions about the quality of life. Discussion with the patient about the outcome of the KOOS questionnaire will point out possible suicidal ideation and will activate a closer follow up of the patient.

8.4 Adverse Events and Serious Adverse Events

8.4.1 Definitions of AE and SAE

AE definition: any untoward medical occurrence in a subject to whom a medicinal product is administered and which does not necessarily have a causal relationship with this treatment CTR article 2 (32). There are

4 grades of AE: mild AE; moderate AE; severe AE and life-threatening AE or disabling AE.

SAE definition: any untoward medical occurrence that at any dose requires inpatient hospitalisation or prolongation of existing hospitalisation, results in persistent or significant disability or incapacity, results in a congenital anomaly or birth defect, is life-threatening, or results in death

Additional details and clarifications for AEs and SAEs are in Appendices 12.1 and 12.2

8.4.2 Time Period and Frequency for Collecting AE and SAE Information

At each follow-up (at the end of the hospital stay, after 6 weeks, after 6, 12 and 24 months and after 5 years, for the operated group and after 6, 12, 24 months and 5 years for the non-operated group) AE and SAE are collected regularly. Since the patient can inform the investigator about AE, or SAE at any time, collecting AE and SAE are performed as soon as known by the investigator. After finishing the trial, the investigator is still reachable for the patient to inform him about any AE or SAE.

8.4.3 Identifying AEs and SAEs

At each follow-up AE and SAE are collected regularly. Since the patient can inform the investigator about AE, or SAE at any time, collecting AE and SAE are performed as soon as known by the investigator. After finishing the trial, the investigator is still reachable for the patient to inform him about any AE or SAE

8.4.4 Recording of AEs and SAEs

AEs and SAEs will be recorded in the electronic patient chart and in the CRF and in the adverse event log/serious adverse event log. Severity and causality and final outcome will be recorded.

Further details on assessing severity and causality of AEs and SAEs are in Appendix 12.3 and 12.4

8.4.5 Follow-up of AEs and SAEs

The adverse event log/serious adverse event log will follow-up all actions taken in respect to solving the adverse event or serious adverse event. Patient will be followed until the AE/SAE is solved either in the hospital or as an out-patient.

8.4.6 Reporting of SAEs

SAEs will be reported in the electronic patient chart, in the CRF and to follow-up in the SAE event log. All SAEs will be reported to the ethic committee and to local authorities (Bundesoberbehörde) at least 15 days after obtaining knowledge of the event. SAEs related to the IMP will be reported to the EudraVigilance Data base.

On the Webpage of the PEI there is a document

(<https://www.pei.de/DE/Arzneimittelsicherheit/gewebevigilanz/meldeformulare/meldeformulare-node.html> Form G1a) to be filled in for :" Meldung des Verdachts einer schwerwiegenden unerwünschten Empfängerreaktion im Zusammenhang mit der Übertragung von Gewebe, Gewebezubereitungen oder Stammzellen gemäß § 63i AMG" this form would be filled and send to the PEI.

8.4.7 Regulatory Reporting Requirements for SAEs

For this clinical trial, the sponsor and the investigator are the same person. The investigator/sponsor must report the following:

SAEs should be reported to the ethic committee and to the authorities (Bundesoberbehörde) immediately after knowledge of the event, but not later than 15 calendar days. Life threatening SAEs must be reported

within 24 h but at least 7 days after being aware of the case. Follow-up-reports must be submitted if the information in the initial submission is incomplete.

8.4.8 Serious and Unexpected Adverse Reaction Reporting

SUSARs which are fatal or life threatening, the sponsor should report at least the minimum information as soon as possible and, in any case, not later than 7 days after being aware of the case to the ethic committee and to the local authorities (Bundesoberbehörde). SUSARs which are not fatal, or life threatening are to be reported within 15 days to the ethic committee and to the local authorities (Bundesoberbehörde). SUSARs must be reported to the EudraVigilance date base electronically and to the PEI using the specified form.

8.4.9 Adverse Events of Special Interest

There are no adverse events of special interest expected.

8.4.10 Disease-related Events or Outcomes Not Qualifying as AEs or SAEs

Disease related events and outcomes, which will be not reported as AE or SAE will be: progression of osteoarthritis up to TKA. This will happen when the treatment failed.

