7 DISCONTINUATION OF TRIAL INTERVENTION AND PARTICIPANT WITHDRAWAL FROM TRIAL

7.1 Discontinuation of Trial Intervention

7.1.1 Criteria for Permanent Discontinuation of Trial Intervention

This is an orthopedic trial. The surgery is the start point and after the surgery there is no further treatment. There are only follow-up visits, which include an MRI (after 6 weeks, 6, 12, 24 months and 5 years in the operated group and after 24 months and 5 years in the non-operated group) and 3 questionnaires (IKDC and KOOS, CRF).

Criteria for permanent discontinuation for **single patients** from the trial are the following:

- Withdrawal of the informed consent
- lost to follow-up,
- premature death
- progression of osteoarthritis up to TKA
- the patient wishes to change to the operated group after a certain time

When withdrawal of the informed consent, premature death or lost to follow-up occurs, data up to the point will be used. If progression of osteoarthritis up to TKA occurs, the treatment is counted as treatment failure. These patients cannot continue the trial. Data up to the point will be used.

If the patient changes his decision and want to be operated at a later time point, the patient can continue the trial, but will be allocated to the other study arm. Data collected up to this point will be used in the first treatment group and then data will be generated in the second treatment group.

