12 APPENDIX: ADVERSE EVENTS AND SERIOUS ADVERSE EVENTS – DEFINITIONS, SEVERITY, AND CAUSALITY

12.1 Further Details and Clarifications on the AE Definition

There are no regional AE requirements. An adverse event log is filled to follow the adverse event until it is solved.

A trial related adverse event is redness, haematoma, swelling, infection of the operated site and pain of the treated knee. This will be recorded in the electronic patient chart and in the CRF.

Progression of osteoarthritis up to TKA does not meet AE definition; it is the normal progression of the disease and will be expected to be more observed in the non-operated group.

The IMP of this clinical trial is human cancellous bone, there is no dose, there are only dimensions of the transplant. Thus, there is no overdose.

Lack of efficacy of the procedure is provided when more than 20% of the procedures fail.

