12.2 Further Details and Clarifications on the SAE Definition

SAEs must be reported immediately to the IRB/IEC except for those SAEs that the protocol identifies as not needing immediate reporting. Additionally SAEs related to the IMP are reported to the EudraVigilance Data base and via the CTIS webpage.

A trial related SAE is an allergic reaction against the IMP.

Progression of osteoarthritis up to TKA does not meet SAE definition; it is the normal progression of the disease and will be expected to be more observed in the non-operated group.

On the Webpage of the PEI there is a document

(<https://www.pei.de/DE/Arzneimittelsicherheit/gewebevigilanz/meldeformulare/meldeformulare-node.html>, Form G1a) to be filled in for :“ Meldung des Verdachts einer schwerwiegenden unerwünschten Empfängerreaktion im Zusammenhang mit der Übertragung von Gewebe, Gewebezubereitungen oder Stammzellen gemäß § 63i AMG“ this form would be filled and send to the PEI.

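### Progression to TKA in an operated knee is kept out of AE/SAE recording with no exception for suspected implant or procedure causation, so its cause is never assessed

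*Protocol*

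**What the plan says.** Section 8.4.10 lists the outcomes that fall outside safety reporting: "Disease related events and outcomes, which will be not reported as AE or SAE will be: progression of osteoarthritis up to TKA". It adds: "This will happen when the treatment failed".

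The appendix gives the reason. Section 12.1: "Progression of osteoarthritis up to TKA does not meet AE definition; it is the normal progression of the disease". Section 12.2: "Progression of osteoarthritis up to TKA does not meet SAE definition; it is the normal progression of the disease". Both sections expect the event more often without surgery. None of the three restricts the exemption to one group or excepts a suspected link to the graft or the operation.

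Section 8.4.1 holds the general definitions. An AE is an untoward occurrence "which does not necessarily have a causal relationship with this treatment". An SAE is "any untoward medical occurrence that at any dose requires inpatient hospitalisation or prolongation of existing hospitalisation, results in persistent or significant disability or incapacity", with further outcome criteria after that.

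Section 7.1.1 classifies the same event for efficacy: "If progression of osteoarthritis up to TKA occurs, the treatment is counted as treatment failure".

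**The concern.** Under section 8.4.1, cause does not decide whether an occurrence is an AE. Sections 12.1 and 12.2 exclude TKA because of a presumed cause, the underlying disease. For an operated knee that presumption is part of what the trial has to find out: the graft is described as novel for this use, and the clinical support cited for the procedure is a case report (sections 2.1, 2.2 and 6.2).

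The exemption also goes further than a reporting waiver. Sections 8.3 and 12.2 allow the protocol to waive notification, or immediate reporting, of certain SAEs. Section 8.4.10 instead removes the event from AE and SAE status altogether.

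What is at stake is the assessment of individual cases. If a graft or the operation contributed to the joint damage that ended in TKA, no planned step would ask the question. Sponsor and investigator are the same person, there is no data monitoring committee (sections 4.1 and 8.3), and only the investigator sees outcome data while the trial runs (section 9.7).

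**Working it through.** The protocol states no figure for this point, so there is none to reproduce. The check has two parts.

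**1. What depends on AE/SAE status**

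| Step | Section | Applies to |
|---|---|---|
| Severity, causality and outcome recorded | 8.4.4 | AEs and SAEs |
| Follow-up until resolved | 8.4.5 | AEs and SAEs |
| Report to ethics committee and authorities; EudraVigilance if related to the product | 8.4.6, 8.4.7 | SAEs |
| SUSAR handling | 8.4.8 | suspected unexpected serious reactions |
| Causality scale | 12.4 | an observed AE |
| Secondary safety endpoint | 3.2 | treatment-related AEs and SAEs |
| Safety analysis | 9.5 | AEs, SAEs and SUSARs |

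An event that is neither an AE nor an SAE reaches none of these steps.

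TKA is captured elsewhere:
- as a secondary endpoint (3.2);
- as an exploratory endpoint with Kaplan-Meier curves and a logrank test in both groups (3.3, 9.4);
- through the complication and reoperation items scheduled at every follow-up visit (1.3);
- as a failure counting towards the 20% rule (7.4, 8.2, 9.2.2, 9.7).

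These routes count the event. None of them calls for a judgement on cause.

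**2. Can the 20% rule stand in for case review?**

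Inputs: 30 operated patients (sections 1.1 and 9.8); re-evaluation when failures exceed 20% (section 8.2). The true TKA rates are assumptions, shown as a range. TKA is taken as the only type of failure.

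Threshold: 0.20 × 30 = 6, so more than 20% means at least 7 failures.

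P(fires) = 1 − Σ (k = 0 to 6) C(30, k) p^k (1 − p)^(30 − k)

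P(at least one TKA) = 1 − (1 − p)^30

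| Assumed true TKA rate p | P(at least one TKA in 30) | P(at least 7 in 30) |
|---|---|---|
| 2.5% | 53.2% | 0.0007% |
| 5% | 78.5% | 0.06% |
| 10% | 95.8% | 2.6% |
| 15% | 99.2% | 15.3% |
| 20% | 99.9% | 39.3% |

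If the rate were taken over the 24 operated patients left after the protocol's 20% loss, the threshold would be 5 (0.20 × 24 = 4.8). The probability would then be 8.5% at p = 10% and 28.7% at p = 15%.

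At an assumed 10%, at least one operated patient would almost certainly reach TKA, yet the rule would fire about once in 40 trials (1/0.026 ≈ 39).

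**Expected workload.** Section 11.1 gives 2.5% for incomplete data due to progression to TKA, without separating the groups. Over all 40 patients this is 0.025 × 40 = 1.0 event. Applied evenly to the operated group it is 0.025 × 30 = 0.75. The even split is an assumption, since sections 12.1 and 12.2 expect more events without surgery.

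**The case against.** The strongest reply is that the protocol exempts a disease outcome because it already captures it as an endpoint, which is a legitimate design choice. Section 8.4.1 itself sends the reader to 12.1 and 12.2 for clarification, so a specific carve-out need not contradict a general definition. Much of this stands. Excluding an endpoint event from AE reporting is not an error in itself. What it does not answer is the lack of any exception for suspected causation in a knee that carries the graft.

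Several stronger readings are tempting, and the protocol does not support them:

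- **Implant-related joint damage never reaches the safety data.** The exemption covers only osteoarthritis progression up to TKA. Pain, swelling and infection of the treated knee are named as trial-related AEs (12.1), and an allergic reaction to the product as a trial-related SAE (12.2). Complications are part of the safety evaluation (section 9) and are compared between groups (9.1). Operated knees have MRI from 6 weeks to 5 years, including extrusion and Outerbridge grade (3.2, 7.1.1). Trouble with the graft could well show before a TKA.
- **TKA plainly meets the SAE definition.** The protocol never says that TKA requires an inpatient stay. That is an assumption. The AE definition applies without it, and 8.4.10 and 12.1 exclude the event even as an AE.
- **Treatment failure and normal disease progression exclude each other.** A treatment meant to prevent progression fails when the disease progresses, so both can be true. The failure label only shows that the protocol ties the event to the treatment's result.
- **The patient is certainly lost to follow-up after TKA.** Section 7.1.1 says such patients cannot continue, but the rescue therapy text under 6.8.2 says they remain in the trial. Those passages need reconciling separately.

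**Conclusion.** The concern holds in a limited form. Sections 8.4.10, 12.1 and 12.2 conflict with section 8.4.1 for operated knees. Their effect is that a TKA in an implanted knee gets no causality grade, no SUSAR assessment and no place in the AE/SAE analysis. It remains visible as an efficacy outcome and may also appear under complications or reoperations.

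The failure rule is a weak substitute for case review: it fires with probability 2.6% at an assumed true TKA rate of 10% and 15.3% at 15%, with 30 operated patients and no other failure type. Other kinds of failure would make it fire more often, but it would still not examine cause.

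Few events are expected, about one in the whole trial at the protocol's own 2.5%. With so few events, a safety signal would have to come from looking at each case rather than from comparing rates. The conflict with the AE definition rests on the text alone; SAE status rests on the assumption of an inpatient stay.

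**What to change.** Reconcile 8.4.10, 12.1 and 12.2 with 8.4.1:

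1. Limit the exemption to never-operated knees. These patients receive no investigational product, and the AE definition in 8.4.1 refers to subjects who have received a medicinal product.
2. For operated knees, including those of patients who cross over, record TKA of the study knee as an SAE. Grade causality for product and procedure under 12.4, and handle the event under 8.4.6 to 8.4.8.
3. Tabulate study-knee TKA separately for both groups and leave it out of the between-group AE/SAE test. Otherwise the event would count as an SAE in one group only and distort the comparison.
4. Leave the treatment-failure count and the Kaplan-Meier analysis as they are.

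The cost is wording in three sections and about one extra SAE form at the protocol's expected rate. The SAE count in the operated group may be slightly higher, which the separate table makes clear.
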